### 8.2.5.3. Statistical Methodology Specification (Part C)

#### Bioavailability of Food Effect

Endpoint (log scale)

 
AUC(0-inf)
 
AUC(0-t) if AUC(0-inf) not available
 
Cmax
 

 

Model Specification

 
For each endpoint a mixed model will be fit with 5 observations per subject expected. The model will contain dose (240mg, 480mg) and prandial state [fed (standard)/delayed fed
 

(standard)/delayed fed (high-fat)/fasted] as a fixed, categorical effect and a random intercept for subject.

 
• A direct product (UN@CS) covariance pattern will be fit using dose and state (in that order) as the effects in the REPEATED statement.
 
• The Kenward & Roger (KR) degrees of freedom approach will be used.
 

Model Checking & Diagnostics

 
• See Section 8.1.5.1.
 

Model Results Presentation

 
• Point estimates and corresponding 90% CI will be computed for the differences in the endpoint for GSK2982772 MR formulation (240 mg or 480 mg) taken in the fed state (test) vs in the fasted state (reference) using the residual error from the model (MSE).
 
• The point and interval estimates on the log-scale will then be exponentially back transformed to give estimates of the ratios of geometric means, <math>F_{rel,FE}</math>, and 90% CI. See Section 10.6.4
 

Endpoint

 
• <math>T_{max}</math>
 

Model Specification

 
• Exact non-parametric Hodges-Lehmann estimation of location shift will be fitted.
 
• Only the dose of GSK2982772 administered under both fed and fasted conditions will be used.
 

Model Results Presentation

 
• GSK2982772 MR formulation in fed (test) state will be compared to fasted (reference) state.
 
• Median difference and 90% CI for median difference will be presented.
 

## Bioavailability of Dose

Endpoint (log scale)

 
• <math>AUC(0-\infty)</math>
 
• <math>AUC(0-t)</math> if <math>AUC(0-\infty)</math> not available
 
• <math>AUC(0-24)</math>
 
• <math>C_{max}</math>
 
• <math>C_{24}</math>
 

Model Specification

 
• For each endpoint a mixed model will be fit with 2 observations per subject expected. The model will contain dose (480 mg and 240 mg in the fasted state) as a fixed, categorical effect, and a random intercept for subject.
 
• The Kenward and Roger method for approximating the denominator degrees of freedom and correcting for bias in the estimated variance-covariance of the fixed effects will be used.
 

Model Checking & Diagnostics

See Section 8.1.5.1.

Model Results Presentation

Point estimates and corresponding 90% CI will be computed for the differences in the endpoint for GSK2982772 MR dose (480 mg vs 240 mg) using the residual error from the model (MSE).

The point and interval estimates on the log-scale will then be exponentially back transformed to give estimates of the ratios of geometric means, <math>F_{relDOSE}</math>, and 90% CI. See Section 10.6.4

Endpoint

Tmax

Model Specification

Exact non-parametric Hodges-Lehmann estimation of location shift will be fitted.

Only GSK2982772 administered at 240 mg and 480 mg.

Model Results Presentation

GSK2982772 MR formulation at 480 mg (test) state will be compared to 240 mg (reference).

Median difference and 90% CI for median difference will be presented.

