## 5. CONSIDERATIONS FOR DATA ANALYSES AND DATA HANDLING CONVENTIONS

### 5.1. Study Treatment & Sub-group Display Descriptors

Treatment Group Descriptions			
RandAll NG		Data Displays for Reporting	
Code	Description	Description	Order in TLF
Part A			
A	GSK2982772 120mg minitab MR RR1 oral single dose	MT-12h 120mg Fasted	2
B	GSK2982772 120mg minitab MR RR2 oral single dose	MT-8h 120mg Fasted	3
C	GSK2982772 120mg IR oral single dose	IR 120mg Fasted	1
D	GSK2982772 120mg minitab MR RR3 oral single dose	MT-12h 120mg Fed (Standard)	4
E	GSK2982772 120mg minitab MR RR4 oral single dose	n/a	5
F	GSK2982772 120mg minitab MR fed state	n/a	6
Part B			
G	GSK2982772 minitab MR Repeat Dose 1	MT-12h 120mg Fasted	1
H	GSK2982772 minitab MR Repeat Dose 2	MT-12h 240mg Fasted	2
J	GSK2982772 minitab MR Repeat Dose 3	MT-12h 300mg Fed (Standard)	3
Part C			
K	GSK2982772 240mg (matrix monolithic) MR oral single dose	MM-12h 240mg Fasted	2
L	GSK2982772 240mg IR oral single dose	IR 240mg Fasted	1
M	GSK2982772 360mg or 480mg (matrix monolithic) MR oral single dose	MM-12h 480mg Fasted	3
N*	GSK2982772 240mg (matrix monolithic) MR fed state	MM-12h 480mg Fed (Standard)	4
P	GSK2982772 360mg or 480mg (matrix monolithic) MR delayed fed (standard meal) or fed (high-fat meal)	MM-12h 480mg Delayed Fed (Standard)	5
Q	GSK2982772 dose tbd (matrix monolithic) MR QD or BID prandial state tbd.	MM-12h 240 mg Delayed Fed (High-Fat)	6

\* The randomization description for Period 4 of Part C (code N) indicates 240 mg, but the label has been updated to 480 mg to reflect the actual treatment administered.

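### The Part C Tmax dose comparison (SAP 8.2.5.3) omits the fasted restriction, so the 480 vs 240 mg shift mixes dose with prandial state; the Part C food-effect Tmax rule does not name its contrasts

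*SAP*

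**What the plan says.** SAP 8.2.5.3, under Bioavailability of Dose, has two blocks.

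- **AUC, Cmax and C24.** "The model will contain dose (480 mg and 240 mg in the fasted state) as a fixed, categorical effect". The expected data are stated: "For each endpoint a mixed model will be fit with 2 observations per subject expected".
- **Tmax.** The method is given as "Exact non-parametric Hodges-Lehmann estimation of location shift will be fitted". The data are selected by "Only GSK2982772 administered at 240 mg and 480 mg". The results line reads "GSK2982772 MR formulation at 480 mg (test) state will be compared to 240 mg (reference". No prandial state and no count of observations per participant are given.

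Under Bioavailability of Food Effect in the same section, the AUC/Cmax model covers all MR regimens ("For each endpoint a mixed model will be fit with 5 observations per subject expected") and has separate levels for fasted, fed standard, delayed standard and delayed high-fat. The Tmax block there selects by "Only the dose of GSK2982772 administered under both fed and fasted conditions will be used" and compares fed (test) with fasted (reference).

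SAP 5.1 gives the regimens as administered. The label for code Q begins "MM-12h 240 mg Delayed Fed (High-Fat". A footnote to that table corrects code N to 480 mg. Regimen letters below are the SAP codes, which differ from the letters in Protocol 7.1.3.

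**The concern.** The Tmax dose rule looks like a restriction, but it separates none of the MR regimens, because 240 and 480 mg are the only doses in Part C. The estimator has no term or stratum for food. Whatever a meal does to Tmax therefore enters the 480 vs 240 mg shift. Food is a realistic source of bias: Protocol 3.1 reports that the slowest minitab showed a food effect, and Part C follows from that finding.

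Tmax is a listed endpoint for both the dose-dependence and the food objective of the MR tablet (SAP 2.2; Protocol 4). A meal-driven change could be read as altered absorption at the higher dose, or could hide one.

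The food-effect Tmax rule raises a related problem. It repeats the Part A wording, where a single dose of 120 mg was used. In Part C both doses were given fasted and with some form of meal, so the rule does not pick out one dose, and it says nothing about which meal is the test condition.

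**Working it through.** **1. Regimens (SAP 5.1, display labels).**

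| Code | Formulation | Dose | State |
|---|---|---|---|
| K | MR | 240 mg | fasted |
| L | IR | 240 mg | fasted |
| M | MR | 480 mg | fasted |
| N | MR | 480 mg | fed standard |
| P | MR | 480 mg | delayed standard |
| Q | MR | 240 mg | delayed high-fat |

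**2. Reproduce the plan's own counts.** MR and fasted gives {K, M}, which is 2 per participant and matches the AUC/Cmax/C24 dose model. All MR gives {K, M, N, P, Q}, which is 5 and matches the food-effect model.

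**3. Apply the Tmax dose rule.** MR at 240 or 480 mg gives {M, N, P} against {K, Q}: 5 regimens, not 2. At the 12 evaluable participants of Protocol 5.2, that is 3 × 12 = 36 records against 2 × 12 = 24. The share given with a meal or delayed meal is 2/3 at 480 mg and 1/2 at 240 mg.

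**4. Look for overlap.** The 480 mg states are fasted, fed standard and delayed standard. The 240 mg MR states are fasted and delayed high-fat. Fasted is the only state in common, so M vs K is the only dose contrast free of food.

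**5. Direction of the bias (illustration).** Suppose there is no dose effect, and the meals in N, P and Q shift Tmax by f_N, f_P and f_Q hours. The difference in pooled means is then

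(f_N + f_P)/3 − f_Q/2.

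Hodges-Lehmann is not a difference of means, so the median of all pairwise differences between the pooled sets was also simulated. The assumptions were 12 participants, fasted MR Tmax 6 h, between-participant SD 1 h, within-participant SD 2 h, values on a 2-h grid and 2,000 replicates. The grid matches the MR sampling schedule; the other Tmax inputs are assumed.

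| f_N / f_P / f_Q (h) | Formula (h) | Simulated pooled shift (h) | Simulated M vs K (h) |
|---|---|---|---|
| 0 / 0 / 0 | 0 | 0.02 | 0.02 |
| 2 / 2 / 2 | 1.33 − 1.00 = 0.33 | 0.25 | 0.00 |
| 4 / 2 / 2 | 2.00 − 1.00 = 1.00 | 1.00 | 0.02 |
| 4 / 4 / 4 | 2.67 − 2.00 = 0.67 | 0.65 | 0.03 |
| 4 / 4 / 0 | 2.67 − 0 = 2.67 | 2.67 | −0.01 |
| −2 / −2 / 0 | −1.33 − 0 = −1.33 | −1.41 | −0.01 |

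The pooled shift follows the meals, in either direction. The fasted contrast stays at zero.

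**6. Food-effect Tmax rule.** Two readings are open. If only code N counts as fed, the contrast is N vs M, and P and Q get no Tmax comparison. If delayed meals count as fed, both doses qualify. The AUC/Cmax results text in the same block supports the second reading: it speaks of 240 or 480 mg taken fed, and the only 240 mg MR regimen with a meal is Q. The block does not choose between them.

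**The case against.** The strongest reply is that the fasted restriction carries over. The Tmax block sits under the same heading as a model limited to fasted dosing. Tables 3.21 and 3.22 are a matched pair with the same dose title. Pooling would also leave three 480 mg values and two 240 mg values per participant, with no rule for combining them, which suggests pooling was never intended. As an account of intent, this is probably right. It does not settle the text: the Tmax block states its own selection rule, that rule does not mention fasting, and neither table entry supplies it.

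Two stronger readings are tempting, and the documents do not support them.

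- **A reader might infer that the IR tablet (L) is also pooled**, because it too was given at 240 mg. The results line names the MR formulation, and the objective concerns the MR tablet. L falls outside the comparison.
- **A reader might infer that food-effect Tmax is reported as one fed-minus-fasted shift merged over all meals.** No sentence directs a merge. Protocol 10.4.1 plans a separate non-parametric Tmax analysis for each MR formulation given fed and fasted, and defines the modelled food contrasts within the same dose. What stands is that the SAP leaves the contrasts unnamed.

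The consequence is also limited. Table 3.14 summarises derived parameters by formulation and prandial state, and Listing 91 gives individual values, so Tmax for each regimen will be visible.

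**Conclusion.** The concern holds. As written, the Tmax dose rule yields {M, N, P} vs {K, Q}, which confounds dose with prandial state. This rests only on SAP 5.1 and 8.2.5.3 and needs no assumption about Tmax. The food-effect Tmax rule is ambiguous in Part C; it is not shown to be wrong.

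The size of the bias is unknown. The hours in the table depend on assumed Tmax values and meal shifts, and show direction only. With equal 2-h meal shifts the bias is about 0.25 h; it becomes large when meals act differently at the two doses. No figure for confidence-interval coverage can be supported from the documents.

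The analysis is secondary and estimation-only, with no formal hypothesis, and the dose comparison of AUC, Cmax and C24 is correctly restricted. The omission is probably inadvertent. It should be corrected because the stated rule gives a misleading estimate for a listed endpoint.

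**What to change.** In SAP 8.2.5.3, replace the two Part C Tmax selection rules with named regimens, using SAP 5.1 codes:

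- **Dose:** MR fasted only, 480 mg (M) vs 240 mg (K).
- **Food, each reported separately within dose:** N vs M, P vs M, Q vs K.

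Each participant then contributes one value per side, so no rule for combining repeated values is needed. At 12 evaluable participants the dose contrast has 12 values against 12. Carry the same lists into the programming notes for Table 3.20 (food) and Table 3.22 (dose).

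The cost is about two lines of SAP text and a matching data filter. No new data are needed, and the AUC and concentration analyses do not change.

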## **10. APPENDICES**

### **10.1. Appendix 1: Protocol Deviation Management**

- Protocol deviations will be tracked by the study team throughout the conduct of the study in accordance with the Protocol Deviation Management Plan.
  - Data will be reviewed prior to freezing the database to ensure all important deviations are captured and categorised on the protocol deviations dataset.
  - This dataset will be the basis for the summaries and listings of protocol deviations.

## 10.2. Appendix 2: Schedule of Activities

### 10.2.1. Protocol Defined Schedule of Events

#### Schedule of Activities for Parts A and C

Procedure	Screening (up to 28 days before Day 1)	Treatment Period 1, 2, 3, 4, 5, 6 Day			Follow-up/Study Discontinuation (7 days post last dose)	Notes a
		-1	1	2		
Informed consent	X					
Inclusion and exclusion criteria 	X					1. Recheck clinical status before 1st dose of study medication.
Demography	X					
Demonstrate ability to swallow size 0-00 capsules	X					
Full physical examination including height and weight	X					
Brief physical examination		X		X 	X	2. Discharge (32 h post-dose for Treatment Period 1, 2, 4, 5 and 6 in Part A and Treatment Period 1, 3, 4, 5 and 6 in Part C 24 h post-dose for Treatment Period 3 in Part A and Treatment Period 2 Part C)
Medical history (includes substance usage) 	X					3. Substances: Drugs, Alcohol, tobacco and caffeine
Past and current medical conditions	X					

Procedure	Screening (up to 28 days before Day 1)	Treatment Period 1, 2, 3, 4, 5, 6 Day			Follow-up/Study Discontinuation (7 days post last dose)	Notes a
		-1	1	2		
Follicle Stimulating Hormone (FSH) (as needed in women of non-childbearing potential only)	X					
Serum pregnancy test (WOCBP only)	X				X	
Urine pregnancy test (WOCBP only)		X				
Human Immunodeficiency Virus (HIV), Hepatitis B and C screening 	X					4. If test otherwise performed within 3 months prior to first dose of study treatment, testing at screening is not required
Tuberculosis (TB) Test	X					
Urine drug screen	X	X				
Alcohol breath test	X	X				
Carbon monoxide breath test	X	X				
Laboratory assessments (haematology, clinical chemistry and urinalysis)	X	X	X 	X 	X	5. Pre-dose (Treatment Period 1 only) and 24 h post-dose Allowable windows in Section 9.4.4
Glomerular filtration rate	X					
C-reactive protein (CRP)	X					

Procedure	Screening (up to 28 days before Day 1)	Treatment Period 1, 2, 3, 4, 5, 6 Day			Follow-up/Study Discontinuation (7 days post last dose)	Notes a
		-1	1	2		
12-lead ECG	X 	X	X 	X 	X	6. In triplicate 7. Pre-dose and 2 and 12 h post-dose 8. 24 h post-dose Allowable windows in Section 9.4.3
Vital signs	X	X	X 	X 	X	9. Pre-dose and 2 and 12 h post-dose 10. 24 h post-dose Allowable windows in Section 9.4.2
Study treatment			X			
AE review		←=====→			X	
Serious AE (SAE) review	X	←=====→			X	
Concomitant medication review		←=====→			X	
PK blood sample collection			X 	X 		11. Time points in Table 2

a The timing of assessments may be amended in Part C if BID dosing is selected for any of the regimens.

## Pharmacokinetic Blood Sample Collection Times for Parts A and C

	Part A Treatment Periods 1, 2, 4, 5 and 6 (MR Formulations) Part C Treatment Periods 1, 3, 4, 5 and 6 (MR Formulations)																	
	Time (h)	Pre-dose	0	2	4	6	8	10	12	14	16	18	20	22	24	26	28	30
Dosing		X																
PK sampling	X		X	X	X	X	X	X	X	X	X	X	X	X	X	X	X	X
Part A: Treatment Period 3 (IR Formulation) Part C: Treatment Period 2 (IR Formulation)																		
Time (h)	Pre-dose	0	0.33	0.66	1	1.5	2	3	4	6	8	10	12	24				
Dosing		X																
PK sampling	X		X	X	X	X	X	X	X	X	X	X	X	X	X	X	X	X

a PK sampling schedule may be amended in Part C if BID dosing is selected for any of the regimens. If BID dosing is employed the number of PK samples may be reduced i.e. some of the samples between 14 and 24 h may not be required. In addition, the 12 h sample will be taken prior to administering the second daily dose.

## Schedule of Activities for Part B

Procedure	Screening (up to 28 days before Day 1)	Treatment Period 1, 2, 3 Day					Follow-up/Study Discontinuation (7 days post last dose)	Notes
		-1	1	2	3	4		
Informed consent	X							
Inclusion and exclusion criteria 	X							1. Recheck clinical status before 1st dose of study medication.
Demography	X							
Demonstrate ability to swallow size 0-00 capsules	X							
Full physical examination including height and weight	X							
Brief physical examination		X				X 	X	2. Discharge (24 h after the last dose)
Medical history (includes substance usage) 	X							3. Substances: Drugs, Alcohol, tobacco and caffeine
Past and current medical conditions	X							
FSH (as needed in women of non-childbearing potential only)	X							
Serum pregnancy test (WOCBP only)	X						X	
Urine pregnancy test (WOCBP only)		X						

Procedure	Screening (up to 28 days before Day 1)	Treatment Period 1, 2, 3 Day					Follow-up/Study Discontinuation (7 days post last dose)	Notes
		-1	1	2	3	4		
HIV, Hepatitis B and C screening 	X							4. If test otherwise performed within 3 months prior to first dose of study treatment, testing at screening is not required
Tuberculosis Test	X							
Urine drug screen	X	X						
Alcohol breath test	X	X						
Carbon monoxide breath test	X	X						
Laboratory assessments (haematology, clinical chemistry and urinalysis)	X	X	X 			X 	X	5. Pre-dose 6. 24 h after the last dose Allowable windows in Section 9.4.4
Glomerular filtration rate	X							
CRP	X							
ANA	X					X 		7. 24 h after the last dose
12-lead ECG	X 	X	X 	X 	X 	X 	X	8. In triplicate 9. Pre-dose and 2 and 12 h post-dose 10. Pre-dose 11. 24 h after the last dose Allowable windows in Section 9.4.3 Time points may be subject to change depending on results from Part A
Vital signs	X	X	X 	X 	X 	X 	X	12. Pre-dose and 2 and 12 h post-dose 13. Pre-dose 14. 24 h after the last dose Allowable windows in Section 9.4.2 Time points may be subject to change depending on results from Part A
Columbia Suicide Risk questionnaire	X		X 			X 		15. Pre-dose 16. 24 h after last dose of each period
Study treatment			X	X	X			
AE review		<=====>					X	
SAE review	X	<=====>					X	
Concomitant medication review		<=====>					X	
PK blood sample collection			X 	X 	X 	X 		17. Time points in Table 4

## Pharmacokinetic Blood Sample Collection Times for Part B

[figure not shown]
Time (h)	Pre-dose	Periods 1, 2 and 3												
		Days 1 and 3												
		0	2	4	6	8	10	12	14	16	18	20	22	24
Dosing a	X													
PK sampling b	X		X	X	X	X	X	X	X	X	X	X	X c	

a Subjects will be dosed on Days 1, 2 and 3; however, no PK samples will be taken post-dose on Day 2

b PK sampling schedule may be amended based upon the PK data from Part A and/or if BID dosing is selected for Part B. If BID dosing is employed the number of PK samples may be reduced i.e. some of the samples between 14 and 24 h may not be required. In addition, the 12 h sample will be taken prior to administering the second daily dose.

c Day 1 24 h post-dose sample should be taken prior to dosing on Day 2.

PK samples should take priority over other procedures scheduled at the same time point. As guidance, the preferred order of assessments is:

Electrocardiograms (ECGs) should be taken prior to vital signs when both measurements are scheduled at the same time point. Other assessments, e.g. physical examinations etc, will be performed within the required time windows. All safety assessments will be timed and performed relative to the start of dosing.

## **10.3. Appendix 3: Assessment Windows**

### **10.3.1. Definitions of Assessment Windows for Analyses**

No Assessment Windows will be defined for Analysis, and summaries and analyses will be based on nominal visits.

## 10.4. Appendix 4: Study/Treatment Phases and Adverse Events

### 10.4.1. Treatment Phases

Assessments and events will be classified according to the time of occurrence relative to dosing.

Treatment Phase	Definition
Pre-Treatment	Date  ≤ Study Treatment Start Date 
On-Treatment	Study Treatment Start Date  < Date  ≤ Study Treatment Stop Date 
Post-Treatment	Date  > Study Treatment Stop Date 

[1] Datetime if Time is present for assessments or events

### 10.4.2. Treatment States

Assessments and events will be classified according to time of occurrence relative to the start and/or stop date of the study treatment.

### 10.4.3. Treatment States for AE Data

Treatment State	Definition
Pre-Treatment	AE Start Date < Study Treatment Start Date
On-Treatment	If AE onset date is on or after treatment start date & on or before treatment stop date. Study Treatment Start Date ≤ AE Start Date ≤ Study Treatment Stop Date
Post-Treatment	If AE onset date is after the treatment stop date. AE Start Date > Study Treatment Stop Date
Onset Time Since 1 st Dose (Days)	If Treatment Start Date > AE Onset Date = AE Onset Date - Treatment Start Date If Treatment Start Date ≤ AE Onset Date = AE Onset Date - Treatment Start Date + 1 Missing otherwise.
Duration (Days)	AE Resolution Date – AE Onset Date + 1
Drug-related	If relationship is marked 'YES' on [Inform/CRF OR value is missing].

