9.4.5. Suicidal Risk Monitoring

GSK2982772 is considered to be a CNS-active drug. There has been some concern that some CNS-active drugs may be associated with an increased risk of suicidal thinking or behaviour when given to some patients with disease. Although this drug has not been shown to be associated with an increased risk of suicidal thinking or behaviour when given to healthy volunteers, GSK considers it important to monitor for such events before or during clinical studies with compounds such as this.

Participants being treated with GSK2982772 should be monitored appropriately for suicidal ideation and behaviour or any other unusual changes in behaviour. Study medication must be immediately discontinued in all participants who experience signs of suicidal ideation or behaviour.

Families and caregivers of patients being treated with GSK2982772 should be alerted about the need to monitor participants for the emergence of unusual changes in behaviour, as well as the emergence of suicidal ideation and behaviour and to report such symptoms immediately to the study Investigator.

At Screening, the 'Baseline/Screening C-SSRS' will be completed in Part B only. Assessments done at pre-dose Day 1 and Day 4, the 'Since Last Visit C-SSRS' will be completed in Part B only. GSK Version 4.1 of both rating scales will be used.

Participants who answer 'yes' to any suicidal behaviour or 'yes' to suicidal ideation Questions 4 or 5 will be referred to their General Practitioner or appropriate psychiatric care and be discontinued from study medication. The Medical Monitor will be notified. If appropriate, an AE or SAE should be reported (see Section 9.2). In addition, the Investigator should complete a Possible Suicidality Related Adverse Event (PSRAE) form to collect detailed information on the circumstances of the reported AEs which, in the Investigator's opinion, are possibly suicidality-related. These may include, but are not limited to, an event involving suicidal ideation, a preparatory act toward imminent suicidal behaviour, a suicide attempt, or a completed suicide.

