## 5.2. Baseline Definitions

For all endpoints (except as noted in baseline definitions) the baseline value will be the latest pre-dose assessment with a non-missing value, including those from unscheduled visits. If time is not collected, Day 1 assessments are assumed to be taken prior to first dose and used as baseline.

Parameter	Study Assessments Considered as Baseline			Baseline Used in Data Display
	Screening	Day -1	Day 1 (Pre-Dose)	
Safety				
Vital signs	X	X	X	Day 1 (Pre-Dose)
12-lead ECG	X	X	X	Day 1 (Pre-Dose)
Laboratory (Haematology, clinical chemistry and urinalysis)	X	X	X	Day 1 (Pre-Dose)

Unless otherwise stated, if baseline data is missing no derivation will be performed and baseline will be set to missing.

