### 7.2. Clinical Laboratory Analyses

Laboratory evaluations including the analyses of Chemistry laboratory tests, Hematology laboratory tests, Urinalysis, and liver function tests will be based on GSK Core Data Standards. The details of the planned displays are in [Appendix 11: List of Data Displays](#).

In addition to GSK Core Data Standards, Lipids (Total Cholesterol and Triglycerides) outside the normal range will be summarised. Other Safety Analyses

The analyses of non-laboratory safety test results including ECGs and vital signs will be based on GSK Core Data Standards, unless otherwise specified. Suicide risk monitoring including analyses of Colombia Suicide Severity Rating Scale (C-SSRS) and Possible Suicidality Related Adverse Event (PSRAE) will be based on GSK Core Data Standards, unless otherwise specified. The details of the planned displays are presented in [Appendix 11: List of Data Displays](#).

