
 
Point estimates and corresponding 90% CI will be computed for the differences in the endpoint between Day 1 and Day 3 for Period 1 (120mg daily), Period 2 (240mg daily), and Period 3 (300mg daily) for GSK2982772 minitab MR dose.
 
The point and interval estimates on the log-scale will then be exponentially back transformed to give estimates of the ratios of geometric means, <math>F_{relDay}</math>, and 90% CI. See Section 10.6.4
 

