2.36.	Safety	LIVER1	Summary of Liver Monitoring/Stopping Event Reporting: Part B	IDSL	SAC
2.37.	Safety	LIVER10	Summary of Hepatobiliary Laboratory Abnormalities: Part B		SAC
ECG					
2.38.	Safety	EG1	Summary of ECG Findings: Part B	IDSL	SAC
2.39.	Safety	EG2	Summary of Change from Baseline in ECG Values by Visit: Part B	IDSL	SAC
2.40.	Safety	CP_EG12	Summary of Maximum Change from Baseline in QTc Values by Category: Part B	IDSL	SAC
Vital Signs					
2.41.	Safety	VS1	Summary of Change From Baseline in Vital Signs by Visit: Part B	ICH E3 Includes Baseline values.	SAC
2.42.	Safety	VS1	Summary of Vital Signs by Visit: Part B		SAC
CSSRS					
2.43.	Safety	CSSRS1	Summary of Subjects with C-SSRS Suicidal Ideation or Behaviour during Treatment: Part B		SAC

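### SAP 10.7.2.1 gives zero or negative durations to adverse events that start after treatment stop and lack a stop day; separately, the SAP leaves open whether Table 2.43 counts the Day 4 C-SSRS after 300 mg

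*SAP*

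**What the plan says.** **AE states and duration.** SAP 10.4.3 makes an AE On-Treatment on this condition: "If AE onset date is on or after treatment start date & on or before treatment stop date". A later onset is Post-Treatment, so the SAP foresees AEs that begin after dosing has ended. Duration is resolution date minus onset date plus 1.

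**Partial dates.** SAP 10.7.2.1 accepts AE dates with only month and year. It says its conventions serve the calculation of time to onset and duration. A missing stop day becomes month-end, or the treatment stop date if month-end falls after it. Nothing ties the result to the onset date. Completely missing dates stay missing.

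**Phases for assessments.** SAP 10.4.1 covers assessments as well as events. A date up to treatment start is Pre-Treatment, a date after start and up to stop is On-Treatment, and anything later is Post-Treatment. The comparison uses "Datetime if Time is present for assessments or events". There is no lag after the last dose. Neither section says whether start and stop belong to the study or to a period.

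**C-SSRS in Part B.** Dosing is on Days 1 to 3 of each period, and SAP 8.2.5.2 gives the order as "Period 1 (120mg daily), Period 2 (240mg daily), and Period 3 (300mg daily"). The schedule in SAP 10.2.1 places the C-SSRS at screening, before dosing on Day 1, and on Day 4, the last being "24 h after last dose of each period". None is scheduled at follow-up. Table 2.43 is titled "Summary of Subjects with C-SSRS Suicidal Ideation or Behaviour during Treatment: Part B". SAP 7.2 says that analyses of the C-SSRS and "Possible Suicidality Related Adverse Event (PSRAE) will be based on GSK Core Data Standards, unless otherwise specified".

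**The concern.** The imputation rule and the AE state rule do not fit together. One recognises AEs that start after treatment stop; the other can end such an AE before it began. A derived duration of zero or less is impossible, and the rule as written produces it without any error in the data.

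The phase rule raises a second, conditional question. The scheduled C-SSRS that follows dosing in Part B comes one day after the last dosing day. In Period 3 that puts it beyond the treatment stop date, and it is the only scheduled C-SSRS after 300 mg, the highest Part B dose. If the C-SSRS summary selects records by the phases in SAP 10.4.1, it cannot show a response from that assessment. Safety and tolerability is a secondary objective, so both derivations should be unambiguous.

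**Working it through.** The plan states no figure for either point, so the check applies its rules directly.

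**1. AE duration**

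Inputs:
- duration = resolution - onset + 1 (SAP 10.4.3);
- missing stop day = the earlier of month-end and treatment stop (SAP 10.7.2.1);
- AEs collected to follow-up (Protocol 9.2.1), which is at least 7 days after the last treatment (Protocol Synopsis, Treatment Groups and Duration).

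Let s be the treatment stop date and s + k the onset, with k of at least 1. The last day of the AE's stop month cannot precede onset, and onset is after s, so the cap always applies and resolution is set to s.

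Duration = s - (s + k) + 1 = 1 - k.

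| k (days after treatment stop) | 1 | 2 | 3 | 4 | 5 | 6 | 7 |
|---|---|---|---|---|---|---|---|
| Duration (days) | 0 | -1 | -2 | -3 | -4 | -5 | -6 |

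Enumerating 365 stop dates, 28 onset lags and 3 possible stop months (365 x 28 x 3 = 30,660 cases) gave 1 - k every time, with a maximum of 0.

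Example: treatment stops 10 January, onset is 11 January, and the stop date is recorded as January only. Without the cap the duration is 31 - 11 + 1 = 21 days; with it, 10 - 11 + 1 = 0.

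The cap also shortens AEs that start on or before s and resolve later. With onset on s (k = 0) and a missing stop day, the result is always 1 day.

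If the cap were a follow-up visit on s + 7 (assumed, with month-end no earlier), duration would be (s + 7) - (s + k) + 1 = 8 - k, that is 7 down to 1 for k = 1 to 7.

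**2. Label of the Day 4 C-SSRS**

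Applying SAP 10.4.1 to Part B:

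| Period and dose | Stop date is study-level | Stop date is per period |
|---|---|---|
| 1, 120 mg | On-Treatment | Post-Treatment |
| 2, 240 mg | On-Treatment | Post-Treatment |
| 3, 300 mg | Post-Treatment | Post-Treatment |
| On-Treatment | 2 of 3 | 0 of 3 |

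Day 4 is a later calendar date than Day 3, so the 300 mg label is the same with dates or datetimes, and with once- or twice-daily dosing. SAP 10.4.3 (onset since first dose), 10.6.1 (study day) and 10.6.2 (treatment breaks) lean towards the study-level reading. SAP 10.4.1 speaks of time relative to dosing and SAP 5.1 lists treatments by period, so the other reading is open.

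**The case against.** The strongest reply concerns consequences. SAP 7.2 sends C-SSRS analyses to the sponsor's data standards, and Table 2.43 uses a standard shell, so its treatment window may be defined there. The schedule also lists Day 4 among the treatment-period days, apart from follow-up, and SAP 10.3.1 bases summaries on nominal visits. On that view Table 2.43 loses nothing. This stands as far as the table goes: its link to SAP 10.4 is not stated. It does not remove the label, because SAP 10.4.1 is the SAP's only phase definition for assessments, and neither a column heading nor nominal visits override it.

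A reader might infer that suicidality data after 300 mg would go unreported, or that AEs after the last dose drop out of the AE tables. The documents support neither. Listings 55 to 57 carry the C-SSRS and PSRAE data, and the main AE tables are titled as covering all AEs. Participant protection under Protocol 8.1.3 and 9.4.5 does not depend on SAP phases.

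On duration, it is fair to say that the case is narrow. Zero or negative values need both an onset after treatment stop and a stop date lacking only its day. Appendix 11 titles no AE-duration summary, and partial dates are listed as captured. That limits the reach but not the error.

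**Conclusion.** Wrong as written, and minor. The duration rule is the main point: every AE that starts k days after treatment stop with only the stop day missing gets 1 - k days, and AEs that run past treatment stop can be truncated. This follows from the SAP's own formulas, and the protocol's AE collection period allows such cases. The effect is confined to derived durations; PK analyses are untouched.

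The C-SSRS point is conditional. The Post-Treatment label after 300 mg is certain on either reading of the stop date. Omission from Table 2.43 follows only if that table uses the SAP 10.4.1 phases, which the SAP does not say. The counts of 2 of 3 and 0 of 3 are labels, not results shown to change. High confidence applies to the label and the duration formula only.

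**What to change.** **SAP 10.7.2.1.** Replace the treatment-stop cap with the follow-up or study end date. Require the imputed stop date to lie within the recorded stop month and never to precede onset. The month condition is needed because SAEs are followed to resolution (Protocol 9.2.3), which can come after follow-up. With follow-up on 17 January and a stop recorded as February, a plain follow-up cap would impute a January date. In that case the cap should give way.

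**SAP 10.4.** Define the on-treatment window for assessments per period: from the first dose of the period to just before the first dose of the next, and through follow-up for the last period. Add a note that Table 2.43 uses this window, so that each Day 4 C-SSRS counts against its own period's regimen. The pre-dose Day 1 form in Periods 2 and 3 is the "Since Last Visit C-SSRS" version (Protocol 9.4.5), so under this window it belongs to the preceding period, which is the time it asks about.

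Leave the baseline rule in SAP 5.2 unchanged: "If time is not collected, Day 1 assessments are assumed to be taken prior to first dose and used as baseline".

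The cost is SAP wording, one programming note, and a change to the phase and AE-duration code. No new data are needed.
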